6.3.4. Daratumumab Dosing Delay and Modification

Dose modification of daratumumab is not permitted. Dose delay is the primary method for managing daratumumab-related toxicities.

6.3.5. Daratumumab Toxicity Management

Cycle Delays

On the first day of each new treatment cycle and before each daratumumab dose, the subject will be evaluated by the treating physician for possible toxicities that may have occurred after the previous dose(s). Toxicities are to be assessed according to NCI-CTCAE, Version 4.03. Dose delays will be based on the toxicity experienced during the previous infusion or newly encountered on Day 1 of a new cycle.

To allow for recovery from toxicity, the study treatment must be held if any of the following criteria are met, regardless of relationship to daratumumab.

- Grade 4 hematologic toxicity, except for Grade 4 lymphopenia
- Grade 3 or thrombocytopenia with (any grade) bleeding
- Febrile neutropenia
- Neutropenia with infection, of any grade
- Grade 3 or higher non-hematologic toxicities with the following exceptions:
 - Grade 3 nausea that responds to antiemetic treatment within 7 days
 - Grade 3 vomiting that responds to antiemetic treatment within 7 days
 - Grade 3 diarrhea that responds to antidiarrheal treatment within 7 days

- Grade 3 fatigue that was present at baseline or that lasts for <7 days after the last administration of daratumumab
- Grade 3 asthenia that was present at baseline or that lasts for <7 days after the last administration of daratumumab

Administration of daratumumab may be restarted upon recovery from toxicity to Grade 2 or baseline, with the exception of Grade 2 laryngeal edema or Grade 2 bronchospasm, which must be fully recovered. If daratumumab administration does not commence within the prespecified window (Table 5) of the scheduled administration date, then the dose will be considered a missed dose. Administration may resume at the next planned dosing date. A missed dose will not be made up.

Table 5: Daratumumab-Related Toxicity Management

Cycles	Frequency	Dose Held	Dosing Re-start
1 and 2	Weekly (q1wk)	>3 days	next planned weekly dosing date
3 to 6	Biweekly (q2wks)	>1 week	next planned biweekly dosing date
7+	Every 4 weeks (q4wks)	>2 weeks	next planned every 4 weeks dosing date

Doses of daratumumab may be delayed up to 4 weeks (Cycle 1 to Cycle 6) or up to 6 weeks (Cycle 7 and beyond). If Day 1 of a cycle is delayed, Day 1 of subsequent cycles should be adjusted accordingly to maintain the 28-day cycle duration. However, if a within-cycle dose is delayed, then the dates of the subsequent within-cycle doses should **not** be adjusted. Any adverse event deemed to be related to daratumumab that requires a dose hold of more than 4 weeks (Cycle 1 to Cycle 6) or more than 6 weeks (Cycle 7 and beyond) will result in permanent discontinuation of daratumumab. If a dose delay occurs, then pharmacokinetic and pharmacodynamic assessments should be performed on the actual administration day of daratumumab, not on the original scheduled administration day.

A daratumumab dose that is held for more than the permitted time (Table 5) from the per-protocol administration date for any reason other than toxicities suspected to be related to daratumumab should be brought to the attention of the sponsor at the earliest possible time. Subjects whose dose was delayed for more than 4 weeks (Cycle 1 to Cycle 6) or more than 6 weeks (Cycle 7 and beyond) should have study treatment discontinued, unless, upon consultation with the sponsor and the review of safety and efficacy, continuation is agreed upon.

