			Cycle 1 Day 1	Cycle 1 Day 8, 15, 22	Cycle 2 Day 1, 8, 15, 22	Cycle 3, 4, 5, 6 Day 1, 15	Cycle 7 until EOT Day 1	EOT Visit Within 30 days after last dose	
Study Procedures		Up to 28 days before first dose							Survival Follow-up Every 16 weeks (+/- 7 days)
Clinical Laboratory Assessments									
Hematology	Hematology laboratory assessments to determine subject eligibility must be performed within 14 days prior to first dose. For Cycle 1 Day 1, clinical laboratory assessments do not need to be repeated if the Screening tests were performed within 5 days of the first dose of study treatment.	X	X ^a	X	Only Day 1 ^a	Only Day 1 ^a	X	X	
Chemistry	Chemistry laboratory assessments to determine subject eligibility must be performed within 14 days prior to first dose. For Cycle 1 Day 1, clinical laboratory assessments do not need to be repeated if the Screening tests were performed within 5 days of the first dose of study treatment.	X	X ^a		Only Day 1 ^a	Only Day 1 ^a	X ^a	X	
Blood type assessment and indirect antiglobulin results	Prior to dosing on Day 1 of Cycle 1 only								
Serum EPO level		X							
Serum ferritin, transferrin saturation		X							
Serology	HIV antibody, hepatitis B surface antigen, and hepatitis C virus antibody	X							
Serum β -hCG or urine pregnancy test	For women of childbearing potential only; must be performed within 14 days prior to first dose	X	Only if clinically indicated						
Ongoing Subject Review									
Concomitant therapy	Continuous from the time of signing ICF until 30 days after the end of dosing or until the start of subsequent anticancer treatment, if earlier	X			Continuous			X	

TIME AND EVENTS SCHEDULE - DARATUMUMAB

PHASE	Notes	Screening Phase	Treatment Phase (4-week cycles +/-3 days)					Posttreatment Follow-up Phase	
		Up to 28 days before first dose	Cycle 1 Day 1	Cycle 1 Day 8, 15, 22	Cycle 2 Day 1, 8, 15, 22	Cycle 3, 4, 5, 6 Day 1, 15	Cycle 7 until EOT Day 1	EOT Visit Within 30 days after last dose	Survival Follow-up Every 16 weeks (+/- 7 days)
Adverse events	Continuous from the time of signing ICF until 30 days after the end of dosing or until the start of subsequent anticancer treatment, if earlier	X	Continuous					X	
Subsequent therapy	Subsequent therapy to be collected throughout survival follow-up period							X	X
Abbreviations: C1D1=Cycle 1, Day 1; CR=complete remission; CyTOF=cytometry by time of flight; EOT=end-of-treatment; EPO=erythropoietin; PD=disease progression; PR=partial remission									

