6.1. Dosing Schedule

Details of the procedures performed during the Treatment Phase are outlined in the Time and Events Schedule. Subjects should start study treatment within 72 hours after randomization. A

window of ± 3 days is allowed for Day 1 of each cycle visits to the clinic. Each cycle is 28 days. The first visit of a cycle should be 4 weeks after the start of the previous cycle. The start of each cycle may occur ± 3 days of the scheduled day in order to accommodate the schedule of the site or subject. Day 1 of subsequent cycles should be adjusted accordingly to maintain the 28-day cycle duration

Study drug is to be administered as described in the Time and Events Schedules.

Talacotuzumab 9 mg/kg will be administered on Days 1 and 15 for all cycles. Daratumumab 16 mg/kg will be administered on Days 1, 8, 15, and 22 (± 24 hours) for Cycles 1 and 2; on Days 1 and 15 (± 24 hours) for Cycles 3 to 6; and on Day 1 (± 24 hours) for all subsequent cycles. Cycles may be delayed due to drug-related toxicities (See Sections 6.2.3 and 6.3.5).

The follow-up of subjects in the study and study data collection will end either 1 year after the last subject is randomized or anytime the sponsor terminates the study. Subjects who are continuing to derive benefit from daratumumab treatment as assessed by their investigator may continue to receive daratumumab according to the protocol. During this period after study data collection has ended, only serious adverse events will be monitored and only entered into the company safety repository as described under Amendment 4 and in the Time and Events Schedule.

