9.2.2. Hemoglobin Assessment

Hemoglobin levels will be measured weekly during the first 8 weeks, at the start of each cycle, and as clinically needed.

For a given subject, the same local laboratory should be used for each hematology assessment throughout the study, to the extent possible. Hematologic improvement-erythroid response (HI-E) is defined as a Hb rise of at least 1.5 g/dL above baseline, measured 28 days or more following the last RBC transfusion or reduction of at least 4 units of RBC transfusions/8 weeks compared with the 8 weeks prior to start of treatment (criterion adapted from IWG 2006).

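### Section 6.3.5 makes Grade 4 hematologic toxicity a mandatory hold, but the daratumumab schedule plans no blood count before Day 15 of Cycles 3-6, and its Cycle 2 entry conflicts with Section 9.2.2

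*Protocol*

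**What the plan says.** **Dosing (Protocol 6.1).** "Daratumumab 16 mg/kg will be administered on Days 1, 8, 15, and 22" of Cycles 1 and 2, then on Days 1 and 15 of Cycles 3-6, and on Day 1 from Cycle 7.

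**Evaluation and hold (Protocol 6.3.5).** On Day 1 of each cycle and "before each daratumumab dose, the subject will be evaluated by the treating physician for possible toxicities". Then "the study treatment must be held if any of the following criteria are met, regardless of relationship to daratumumab", and the list opens with "Grade 4 hematologic toxicity, except for Grade 4 lymphopenia". The same section also says: "Dose delays will be based on the toxicity experienced during the previous infusion or newly encountered on Day 1 of a new cycle".

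**Planned counts (daratumumab Time and Events Schedule, Hematology row, whose note begins "Hematology laboratory assessments to determine subject eligibility must be performed within 14 days prior to first dose").** A count is marked on Days 1, 8, 15 and 22 of Cycle 1. The Cycle 2 cell and the Cycles 3-6 cell each restrict the count to Day 1. Section 9.5 places platelets and absolute neutrophil count (ANC) in this hematology panel.

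**Hemoglobin (Protocol 9.2.2).** "Hemoglobin levels will be measured weekly during the first 8 weeks, at the start of each cycle, and as clinically needed". Neither platelets nor ANC is named there.

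**Related provisions.** Section 9.1.3 has laboratory results reviewed before dosing. Section 9.5 wants required tests within 48 hours of the visit. Section 9.1.1 permits unscheduled samples for safety. Section 9.2.1 collects a platelet count, but no ANC, before a transfusion.

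**The concern.** A mandatory hold works only if the information that triggers it is available when the dose is given. Febrile neutropenia, neutropenia with infection, and thrombocytopenia with bleeding announce themselves clinically and would prompt a test. Grade 4 neutropenia or thrombocytopenia without symptoms does not. If no count is planned before an infusion, a site can comply with the schedule and still give a dose that Section 6.3.5 says must be held.

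Section 16.1 cites the cytopenias of MDS as the reason for routine hematology monitoring. Subjects in a transfusion-free period have no counts taken before red-cell transfusions, so they depend most on the schedule.

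The talacotuzumab Hematology row plans a predose count on every dosing day, although that drug's delay criteria (Section 6.2.3) contain no stand-alone Grade 4 hematologic hold. The daratumumab arm has the count-based hold and the thinner count schedule, and since Amendment 3 it is the only arm enrolling. The protocol gives no reason for the difference.

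**Working it through.** The documents give no figure for this, so the check is a direct enumeration.

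**Inputs.** Infusion days: Protocol 6.1. Planned counts: Hematology row of the daratumumab schedule. Weekly hemoglobin in Weeks 1-8: Protocol 9.2.2. The Cycle 1 Day 8, 15 and 22 cells lack the predose footnote; they are counted as covered because Section 9.1.3 makes visit procedures predose by default.

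| Cycle | Infusion days | Infusions | With a planned count | Without |
|---|---|---|---|---|
| 1 | 1, 8, 15, 22 | 4 | 4 | 0 |
| 2 | 1, 8, 15, 22 | 4 | 1 | 3 |
| 3-6 | 1, 15 in each | 8 | 4 | 4 |
| Total | | 16 | 9 | 7 |

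Cross-check on the total: 8 weekly infusions (Weeks 1-8) plus 8 two-weekly infusions (Weeks 9-24) = 16.

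**Reading A: the weekly draws of Section 9.2.2 are full panels.** Cycle 2 is then covered. Day 15 of Cycles 3-6 (study days 71, 99, 127 and 155) remains uncovered: 4/16 = 25%. The age of the latest planned count is 15 - 1 = 14 days.

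**Reading B: the weekly draws are hemoglobin only.** Cycle 2 Days 8, 15 and 22 (study days 36, 43 and 50) are uncovered as well: 7/16 = 43.8%. The latest planned counts at those three infusions are 8 - 1 = 7, 15 - 1 = 14 and 22 - 1 = 21 days old.

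**Exposure within a 56-day TI period.** There are 85 possible start days (study days 29 to 113) for a 56-day window lying wholly inside Cycles 2-6.

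- Reading A: 1 uncovered infusion in 15 windows and 2 in 70.
- Reading B: 2 uncovered in 63 windows, 3 in 14 and 4 in 8.

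**Do other provisions supply the missing count?**

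- Section 9.1.3 requires review of results but schedules no test. Where none is planned, there may be nothing new to review.
- Section 9.1.1 permits unscheduled samples without requiring them.
- Section 9.2.1 gives platelets but not ANC, and only when a transfusion takes place.
- From Cycle 7, dosing is on Day 1 only and each dose has a count, so the gap is confined to Cycles 2-6.

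**The case against.** The best defence is that the plan can be read coherently: laboratory screening on Day 1, clinical evaluation at mid-cycle doses, and extra tests as needed. Section 6.3.5 asks for an evaluation by the physician, not for a blood count. Its sentence on the basis for delays, which names the previous infusion and Day 1 of a cycle, fits a Day 1 panel. This stands in part: a reader might infer a flat contradiction, and that sentence makes the conflict softer than that. It does not cancel the evaluation before each dose or the unqualified hold beside it.

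A second objection concerns size. A reader might take 7 of 16, and counts up to 21 days old, as the finding. The documents do not establish that. After planning the weekly hemoglobin, Section 9.2.2 goes on to ask for the same laboratory at every hematology assessment, which suggests that these draws are hematology assessments; Section 9.5 includes platelets and ANC in hematology. This is not proof, but it makes 4 of 16 the better supported figure. The higher figure holds only if the draws are hemoglobin alone.

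A third objection is that no harm is shown. Entry requires ANC of at least 1.0 and platelets of at least 50 x 10^9/L without support, and the daratumumab risks listed in Section 1.1 do not include myelosuppression. That is fair. On the other side, Attachment 9 lists cytopenias as events expected from the disease itself.

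**Conclusion.** The point holds as a gap in planned safety monitoring that is cheap to close. On either reading of Section 9.2.2, the four Day 15 infusions of Cycles 3-6 have no planned platelet count or ANC, and the latest planned count is nominally 14 days old. On the hemoglobin-only reading, three Cycle 2 infusions are added, for 7 of 16. On either reading the Cycle 2 cell and Section 9.2.2 disagree and need to be aligned.

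The consequence is limited to symptomless Grade 4 neutropenia or thrombocytopenia that arises between counts. Its frequency is not in the documents and none is assumed here. The gap lies in what is planned; nothing bars an investigator from drawing a count.

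A reader might also infer that the efficacy result is at risk. The documents do not support that: TI is defined by transfusions, and neither the sample size nor the decision rule uses these counts.

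**What to change.** 1. **Daratumumab Time and Events Schedule, Hematology row.** Require a predose count on Days 1, 8, 15 and 22 of Cycle 2 and on Days 1 and 15 of Cycles 3-6. State that the weekly draws of Section 9.2.2 are full hematology panels, so that the two places agree.
2. **Section 6.3.5.** Replace the sentence that ties delays to the previous infusion or Day 1 of a cycle with: *Dose delays will be based on toxicity present at the evaluation before each dose, including the predose blood count.* Basing it on toxicity present at the evaluation avoids holding a dose for something already resolved.

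**Cost.** Four extra counts per subject if Section 9.2.2 is already run as a full panel (4 x 30 = 120 for 30 subjects), and seven if not (7 x 30 = 210). All fall at infusion visits already planned. At an assumed 3-5 mL per draw, four counts add 12-20 mL and seven add 21-35 mL to the roughly 330 mL planned over 8 cycles (12/330 = 3.6% to 35/330 = 10.6%).

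Some further doses will be held. A hold beyond the Table 5 window (more than 3 days in Cycle 2, more than 1 week in Cycles 3-6) loses that dose, which is not made up: 1/16 = 6.3% of the Cycle 1-6 infusions each time. The number of such holds cannot be derived from the documents.

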6.3.6. Guidelines for Daratumumab Infusion-Related Reactions

Subjects should be carefully observed during infusions.

Trained study staff at the clinic should be prepared to intervene in case of any infusion reactions, and resources necessary for resuscitation must be available. Attention to staffing should be considered when multiple subjects will be dosed at the same time.

For infusion reactions of any grade/severity, immediately interrupt the daratumumab infusion and manage symptoms. Management of infusion reactions may further require reduction in the rate of infusion, or treatment discontinuation of daratumumab (see [Table 6](#)).

Table 6: Management of Daratumumab Infusion-related Reactions

Severity <small>[per CTCAE 4.03]</small>	Recommended action
Grade 1 or Grade 2	
 Interrupt infusion and manage symptoms Once reaction symptoms resolve, resume the infusion at no more than half the rate at which the reaction occurred. If patient does not experience any further reaction symptoms, infusion rate escalation may resume at increments and intervals as appropriate as outlined in Table 3.
Grade 3	
 Interrupt infusion and manage symptoms Once reaction symptoms resolve, consider restarting the infusion at no more than half the rate at which the reaction occurred. If the subject does not experience additional symptoms, resume infusion rate escalation at increments and intervals as outlined in Table 3. Repeat the procedure above in the event of recurrence of Grade 3 symptoms. Permanently discontinue daratumumab upon the third occurrence of a Grade 3 or greater infusion-related reaction.
Grade 4	
 Permanently discontinue daratumumab treatment and manage symptoms

7. TREATMENT COMPLIANCE

Talacotuzumab and daratumumab will be administered by qualified site staff, and each administration will be recorded in the eCRF. Following Amendment 4 and either 1 year after the last subject is randomized or anytime the sponsor terminates the study (whichever occurs first), the eCRFs will be closed.

8. PRESTUDY AND CONCOMITANT THERAPY

8.1. Prestudy Therapy

Prestudy MDS therapies administered up to 30 days before first dose of study drug must be recorded at screening. Transfusions up to 16 weeks prior to randomization also must be recorded at screening.

8.2. Concomitant Medications

Subjects should receive supportive care as clinically indicated. This includes blood product support (blood transfusions and use of granulocyte colony stimulating growth factors), anti-diarrheals, anti-emetics, analgesics, anti-infective treatment, and treatment of other medical conditions.

The following medications are prohibited during the study: ESA therapy, chemotherapy (anticancer), immunomodulatory drugs, immunotherapy, experimental therapy, and radiotherapy. Systemic use of corticosteroids in excess of prednisone 20 mg/day or its equivalent for more than

10 days is prohibited unless reviewed and approved by the sponsor. Long-term, chronic use of corticosteroids at any dose should also be reviewed and approved by the sponsor. Corticosteroids used as premedication are permitted. The sponsor must be notified in advance (or as soon as possible thereafter) of any instances in which prohibited therapies are administered.

All concomitant therapies (prescription or over-the-counter medications, including vaccines, vitamins, herbal supplements), including growth factors, transfusions, anti-infectives (antibacterials, antivirals, and antimycotics), corticosteroids, anti-arrhythmics and other cardiac supportive therapy, anti-histamines, anti-emetics, anti-diarrheals, and anti-coagulants must be recorded throughout the study beginning with signing of the ICF to 30 days after the end of dosing or until the start of subsequent anticancer treatment, if earlier. Modification of an effective preexisting therapy should not be made for the explicit purpose of entering a subject into the study. Concomitant therapies should be recorded beyond 30 days after the last dose of study treatment only in conjunction with new or worsening adverse events or serious adverse events that meet the criteria outlined in Section 12.3.2, Serious Adverse Events. The follow-up of subjects in the study and study data collection will end either 1 year after the last subject is randomized or anytime the sponsor terminates the study. Subjects who are continuing to derive benefit from daratumumab treatment as assessed by their investigator may continue to receive daratumumab according to the protocol. During this period after study data collection has ended, only serious adverse events will be monitored and only entered into the company safety repository as described under Amendment 4 and in the Time and Events Schedule.

9. STUDY EVALUATIONS

The follow-up of subjects in the study and study data collection will end either 1 year after the last subject is randomized or anytime the sponsor terminates the study. Subjects who are continuing to derive benefit from daratumumab treatment as assessed by their investigator may continue to receive daratumumab according to the protocol. During this period after study data collection has ended, only serious adverse events will be monitored and only entered into the company safety repository as described under Amendment 4 and in the Time and Events Schedule.

9.1. Study Procedures

9.1.1. Overview

The Time and Events Schedule summarize the frequency and timing of efficacy, PK, immunogenicity, biomarker, and safety measurements applicable to this study.

If multiple assessments are scheduled for the same timepoint, it is recommended that procedures be performed in the following sequence: ECG, vital signs/physical exam, bone marrow assessments/clinical laboratory assessments/peripheral blood sampling for central lab submission, response assessment and other subject review data collection, study drug administration. Blood collections for PK assessments should be kept as close to the specified time as possible. Other measurements may be done earlier than specified timepoints if needed. Actual dates and times of assessments will be recorded in the source documentation and eCRF.

The total blood volume to be collected from each subject will be approximately 330 mL for subjects completing 8 cycles. Repeat or unscheduled samples may be taken for safety reasons or for technical issues with the samples.

An indwelling intravenous cannula may be used for blood sample collection. If a mandarin (obturator) is used, blood loss due to discard is not expected.

Additional serum or urine pregnancy tests may be performed, as determined necessary by the investigator or required by local regulation, to establish the absence of pregnancy at any time during the subject's participation in the study. Repeat or unscheduled samples may be taken for safety reasons or technical issues with the samples.

9.1.2. Screening Phase

Screening procedures will be performed within 28 days before randomization, as described in the Time and Events Schedules.

9.1.3. Open-Label Treatment Phase

The Treatment Phase will begin on Day 1 of Cycle 1 and will continue until discontinuation of study drug.

Treatment Phase

A treatment cycle is defined as 28 days. Details of the procedures performed during the Treatment Phase are outlined in the Time and Events Schedules. Subjects will be monitored for adverse events, laboratory abnormalities, hematologic improvement, reduction in transfusion requirement, and clinical response. All Treatment Phase visit procedures are to be performed predose, unless otherwise specified, and laboratory test results must be reviewed prior to administering study drug. Adverse events and changes to concomitant medications will be recorded. The investigator will assess subject response to therapy using the efficacy measurements and disease response criteria according to the IWG 2006 ([Attachment 6](#)). If a subject develops features of response (eg, recovery from all cytopenias) and CR or PR are clinically suspected at a time not specified on the Time and Events Schedules, then all required disease assessments should be performed. In order to confirm a CR or PR per IWG 2006 criteria, all disease assessments including bone marrow aspirate should be repeated 4-8 weeks from time of CR or PR. If progressive disease is diagnosed, or the subject discontinues study drug for other reasons, then the subject will complete the End-of-Treatment Visit within 30 days after the last dose of study drug, and enter the Posttreatment Follow-up Phase.

End of Treatment/Early Withdrawal

An End-of-Treatment Visit will be scheduled within 30 days after the last dose of study drug for all subjects, including those who discontinued study drug for any reason, except for those lost to follow-up, death, or withdrawal of consent for study participation. Subjects who discontinued study drug due to disease progression, adverse event, lack of response, or other reasons and enter the Posttreatment Follow-up Phase should have the End-of-Treatment Visit completed before starting any subsequent MDS treatment. If a subject is unable to return to the site for the End-of-

Treatment Visit, then the subject should be contacted to collect adverse events that occur within 30 days after the last dose of the last study drug. Additional information on reporting adverse events may be found in Section 12.3.1.

